13.2 Adverse Event Reporting Period

The AE reporting period will begin following the first dose of BGB324 (Run-in Cohort) or erlotinib (Arms A, B, and C) and will end 28 days after the last dose of BGB324. If study drug-related toxicities continue beyond this period, patients will be followed until these toxicities have resolved to ≤Grade 1 or less, stabilized or returned to baseline. Any study drug-related SAEs will be collected indefinitely.

Any SAEs occurring between informed consent and the first dose of BGB324 or erlotinib must also be reported to the Sponsor according to the process in Section 13.5 and also recorded on the eCRF if the patient receives study treatment.

Investigators will seek information on AEs at each patient contact.

All AEs, whether reported by the patient or noted by study personnel, will be recorded in the patient's medical record and in the AE eCRF. A consistent methodology of non-directive questioning should be adopted for eliciting AE information at all patient evaluation time points. Examples of non-directive questions include the following:

- How have you felt since your last clinic visit?
- Have you had any new or changed health problems since you were last here?

13.3 Assessment of Adverse Events

13.3.1 Assessment of severity of adverse events

The AE severity grading scale for the NCI CTCAE Version 4.03 (Appendix 4) will be used for assessing AE severity.

For AEs not specifically listed in the NCI CTCAE, the guidelines in Table 9 will be used for assessing severity.

Table 9 Guidelines for Assessment of Severity for Adverse Events not Listed in CTCAE

Grade	Guideline
Grade 1	Mild; asymptomatic or mild symptoms; clinical or diagnostic observations only; or intervention not indicated
Grade 2	Moderate; minimal, local, or non-invasive intervention indicated; or limiting age-appropriate instrumental activities of daily living ^a
Grade 3	Severe or medically significant, but not immediately life-threatening; hospitalization or prolongation of hospitalization indicated; disabling; or limiting self-care activities of daily living ^{b,c}
Grade 4	Life-threatening consequences or urgent intervention indicated ^d
Grade 5	Death related to adverse event ^d

a. Instrumental activities of daily living refer to preparing meals, shopping for groceries or clothes, using the telephone, managing money, etc.

b. Examples of self-care activities of daily living include bathing, dressing and undressing, feeding one's self, using the toilet, and taking medications, as performed by patients who are not bedridden.

c. If an event is assessed as a "significant medical event," it must be reported as a serious adverse event per the definition of serious adverse event in Section 113.1.2.

d. Grade 4 and 5 events must be reported as serious adverse events per the definition of serious adverse event in Section 13.1.2.

13.3.2 Assessment of causality of adverse events

Investigators should use their knowledge of the patient, the circumstances surrounding the event, and an evaluation of any potential alternative causes to determine whether or not an AE is considered to be related to BGB324 and/or related to erlotinib indicating "suspected" or "not related" accordingly. The following guidance should be taken into consideration:

- Temporal relationship of event onset to the initiation of study drug.
- Course of the event, considering especially the effects of dose reduction, discontinuation of study drug, or reintroduction of study drug (where applicable).
- Known association of the event with the study drug or with similar treatments.
- Known association of the event with the disease under study.
- Presence of risk factors in the patient or use of concomitant medications known to increase the occurrence of the event.
- Presence of non-treatment-related factors that are known to be associated with the occurrence of the event.

Causality will be assessed individually for each protocol-mandated treatment.

13.4 Recording Adverse Events

Investigators should use correct medical terminology and concepts when recording AEs on the AE eCRF. Colloquialisms and abbreviations should be avoided.

Only one AE term should be recorded in the event field on the AE eCRF.

A diagnosis (if known) should be recorded on the AE eCRF rather than individual signs and symptoms (e.g., record only liver failure or hepatitis rather than jaundice, asterixis and elevated transaminases). However, if a constellation of signs and/or symptoms cannot be medically characterized as a single diagnosis or syndrome at the time of reporting, each individual event should be recorded on the AE eCRF. If a diagnosis is subsequently established, all previously reported AEs based on signs and symptoms should be nullified and replaced by one AE report based on the single diagnosis, with a starting date that corresponds to the starting date of the first symptom of the eventual diagnosis.

A pre-existing medical condition which is present at the start of the study and described in the Medical History eCRF, should only be recorded as an AE or SAE if the frequency, severity, or character of the condition worsens during the study. When recording such events on the AE eCRF, it is important to convey the concept that the pre-existing condition has changed by including applicable descriptors (e.g. "more frequent headaches").

13.4.1 Adverse events occurring secondary to other events

In general, AEs occurring secondary to other events (e.g., cascade events or clinical sequelae) should be identified by their primary cause, with the exception of severe or serious secondary events. However, medically significant AEs occurring secondary to an initiating event that are separated in time should be recorded as independent events on the AE eCRF.

For example:

- If vomiting results in mild dehydration with no additional treatment in a healthy adult, only vomiting should be reported on the eCRF.
- If vomiting results in severe dehydration, both events should be reported separately on the eCRF.
- If a severe hemorrhage leads to renal failure, both events should be reported separately in the eCRF.
- If dizziness leads to a fall and subsequent fracture, all 3 events should be reported separately on the eCRF.

- If neutropenia is accompanied by a mild, non-serious infection, only neutropenia should be reported on the eCRF.
- If neutropenia is accompanied by a severe or serious infection, both events should be reported separately on the eCRF.

All AEs should be recorded separately on the AE eCRF if it is unclear as to whether the events are associated.

13.4.2 Persistent and recurrent adverse events

A persistent AE is one that extends continuously, without resolution, between patient evaluation time points. Such events should only be recorded once on the AE eCRF. The initial severity of the event should be recorded and the severity should be updated to reflect the most extreme severity any time the event worsens. If the event becomes serious, the AE eCRF should be updated to reflect this. A recurrent AE is one that resolves between patient evaluation time points and subsequently recurs. Each recurrence of an AE should be recorded separately on the AE eCRF.

13.4.3 Abnormal laboratory and ECG values

Not every laboratory abnormality qualifies as an AE.

A laboratory test result should be reported as an AE if it is assessed to be clinically significant. Suggested criteria for the assessment of clinical significance are:

- Is accompanied by clinical symptoms.
- Results in a change in study treatment (e.g., dosage modification, treatment interruption or treatment discontinuation).
- Results in a medical intervention (e.g., potassium supplementation for hypokalemia) or a change in concomitant therapy.
- Requires more frequent follow-up assessments, further diagnostic investigation, etc.
- Is judged as clinically significant in the Investigator's opinion.

Abnormal laboratory results clearly consistent with the pattern of NSCLC disease or progression do not need to be reported as an AE.

It is the Investigator's responsibility to review all laboratory findings. Medical and scientific judgment should be exercised in deciding whether an isolated laboratory abnormality should be classified as an AE. If a clinically significant laboratory abnormality is a sign of a disease or syndrome (e.g., alkaline phosphatase and bilirubin 5 times the ULN associated with cholecystitis), only the diagnosis (i.e., cholecystitis) should be recorded on the AE eCRF. If a clinically significant laboratory abnormality is not a sign of a disease or syndrome, the abnormality itself should be recorded on the AE eCRF, along with a descriptor indicating if the test result is above or below the normal range (e.g., "elevated potassium," as opposed to "abnormal potassium"). If the laboratory abnormality can be characterized by a precise clinical term per standard definitions, the clinical term should be recorded as the AE. For example, an elevated serum potassium level of 7.0 mEq/L should be recorded as hyperkalemia.

Observations of the same clinically significant laboratory abnormality from visit to visit should not be repeatedly recorded on the AE eCRF, unless the etiology changes. The initial severity of the event should be recorded and the severity or seriousness should be updated any time the event worsens.

13.4.4 Abnormal vital sign values

Not every vital sign abnormality qualifies as an AE. A vital sign result should be reported as an AE if it meets any of the following criteria:

- Is accompanied by clinical symptoms.

- Results in a change in study treatment (e.g., dosage modification, treatment interruption or treatment discontinuation).
- Results in a medical intervention or a change in concomitant therapy.
- Is judged as clinically significant in the Investigator's opinion.

It is the Investigator's responsibility to review all vital sign findings. Medical and scientific judgment should be exercised in deciding whether an isolated vital sign abnormality should be classified as an AE. If a clinically significant vital sign abnormality is a sign of a disease or syndrome (e.g., high blood pressure), only the diagnosis (i.e., hypertension) should be recorded on the AE eCRF.

Observations of the same clinically significant vital sign abnormality from visit to visit should not be repeatedly recorded on the AE eCRF unless the etiology changes. The initial severity of the event should be recorded, and the severity or seriousness should be updated any time the event worsens.

13.4.5 Abnormal liver function tests

An AE meeting the following criteria should be reported to the Sponsor within 24 hours of its initial discovery:

An increase in ALT or AST greater than 3.0 times the ULN accompanied by an increase in serum bilirubin at least 2.0 times the ULN or in the presence of clinical jaundice in the absence of any non-drug related cause such as viral hepatitis.

The event must then be reported to the Regulatory Authority following the process for SAEs (see Section 13.6).

13.4.6 Deaths

Deaths that occur during the AE reporting period that are attributed by the Investigator solely to cancer progression should be recorded only on the End of Treatment eCRF and not as an SAE. All other on-study deaths, regardless of relationship to study drug, must be recorded on the AE eCRF and immediately reported to the Sponsor. Death should be considered an outcome and not a distinct event.

The event or condition that caused or contributed to the fatal outcome should be recorded as the single medical concept on the AE eCRF. Generally, only 1 such event should be reported. The term *sudden death* should only be used for the occurrence of an abrupt and unexpected death due to presumed cardiac causes in a patient with or without pre-existing heart disease, within 1 hour of the onset of acute symptoms or, in the case of an unwitnessed death, within 24 hours after the patient was last seen alive and stable. If the cause of death is unknown and cannot be ascertained at the time of reporting, the term *unexplained death* should be recorded on the AE eCRF. If the cause of death later becomes available (e.g., after autopsy), the term *unexplained death* should be replaced by the established cause of death.

13.4.7 Hospitalization or prolonged hospitalization

Any AE that results in hospitalization or prolonged hospitalization should be documented and reported as an SAE, except as outlined below. The following hospitalization scenarios are not considered to be SAEs:

- Hospitalization for respite care.
- Hospitalization for a pre-existing condition, provided that all of the following criteria are met:
 - The hospitalization was planned prior to the study or was scheduled during the study when elective surgery became necessary because of the expected normal progression of the disease;
 - The patient has not suffered an AE.

- Hospitalization due solely to progression of the underlying cancer.

13.4.8 Overdoses

Study drug overdose is the accidental or intentional use of the drug in an amount higher than the dose being studied. An overdose or incorrect administration of study drug is not an AE unless it results in untoward medical effects. An overdose is defined by a boundary of 15% above the prescribed dose of any medicinal product.

Any study drug overdose or incorrect administration of study drug should be noted on the Study Drug Administration eCRF. All AEs associated with an overdose or incorrect administration of study drug should be recorded on the AE eCRF. If the associated AE fulfills serious criteria, the event should be reported to the Sponsor immediately (i.e., no more than 24 hours after learning of the event).

13.5 Reporting of Serious Adverse Events

Any SAE experienced by a patient between the time of consent and 28 days after the last dose of BGB324 is to be recorded on an SAE Report Form within 24 hours of knowledge by the Investigator of its occurrence, regardless of the severity and causality of the event. Study drug-related SAEs should continue to be reported indefinitely.

The SAE Report Form should be faxed or e-mailed to the Chiltern Pharmacovigilance Group.

[contact]

Fax: + [contact]

A telephone report may only be made in exceptional circumstances and must be followed by completion of the SAE Report Form within 1 working day. Where applicable, information from relevant hospital case records and post-mortem reports should be obtained.

All SAEs that have not resolved by the EOS, or that have not resolved upon the patient's discontinuation from the study, must be followed until any of the following occur:

- The event resolves.
- The event stabilizes.
- The event returns to baseline status.
- The event can be attributed to agents other than study treatment or to factors unrelated to study conduct.
- It becomes unlikely that any additional information can be obtained.

13.6 Immediate Reporting of Serious Adverse Events

Expedited safety reporting within this clinical study complies with the ICH Guideline for Clinical Safety Data Management: Definitions and Standards for Expedited Reporting (E2A), investigational new drug (IND) application safety reporting (under 21CFR312.32), and with applicable local regulatory requirements.

The Sponsor assumes responsibility for appropriate reporting of AEs to the Regulatory Authorities and Institutional Review Boards (IRB). Although this responsibility can be delegated to the Sponsor's Clinical Research organization (CRO), the Sponsor retains ultimate responsibility for safety reporting.

All SAEs that are unexpected and associated with the use of the investigational product are classified as suspected, unexpected serious adverse reactions (SUSARs) and will be reported to the IRBs, Regulatory Authorities and to all investigational sites according to local requirements.

Any safety information from other observations that could change the risk-benefit evaluation of BGB324 should be promptly communicated to the Regulatory Authorities and IRBs.

Any other SUSARs associated with BGB324 should be reported as soon as the Sponsor becomes aware of them, including SUSARs which occur in another clinical study conducted by the same Sponsor or which are identified by spontaneous reports, a publication, or which are transmitted to the Sponsor by another Regulatory Authority.

Other safety issues that also qualify for expedited reporting where they might materially alter the current benefit-risk assessment of the BGB324 (sufficient to consider changes in the administration or in the overall conduct of the trial), include:

- An increase in the rate of occurrence of an expected serious adverse reaction, which is judged to be clinically important.
- Post-study SUSARs that occur after the patient has completed a clinical trial and are reported by the Investigator to the Sponsor.
- New events relating to the conduct of the trial or the development of BGB324 likely to affect the safety of the patients, such as:
 - An SAE which could be associated with study procedures and which could modify the conduct of the study;
 - A major safety finding which differs from the underlying disease.

Expedited reporting is not usually required for reactions which are serious but expected, and it is inappropriate to report events that are considered unrelated to the investigational product. The cause of death of a patient in a clinical study, unless it is associated with disease progression, is considered a SAE whether the event is expected or associated with the investigational agent.

13.7 Procedures for Handling Special Situations

13.7.1 Pregnancy

In the event of a pregnancy occurring in female patients, or in the partners of male patients during the study, the pregnancy must be reported to:

the Chiltern Pharmacovigilance Group (fax + [contact] or email [contact]

by the investigational staff within **1 working day** of their knowledge of the event using a Pregnancy Notification Form.

The reporting period for pregnancies will start with the first administration of BGB324 and end 28 days after the final administration of BGB324.

Any female patients who become pregnant while taking part in the study will be withdrawn; a male patient whose partner becomes pregnant can remain in the study. Female partners of male patients will be asked to provide details of the pregnancy (may be subject to additional consent).

A patient who completes or withdraws from the trial before the full term of the pregnancy will be asked to consent to provision of follow-up information about the pregnancy and its outcome.

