8.9 End-of-Study Visit

Patients will return to the study site for an EOS visit 28 days after the last dose of study drug (or at study withdrawal) according to Section 10.1.5 and Table 5.

If BGB324-related toxicities continue beyond this follow-up period, patients will be followed until all BGB324-related toxicities have resolved to ≤Grade 1, stabilized or returned to baseline. If necessary, follow-up monitoring for AEs may be conducted over the telephone.

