9 SELECTION OF PATIENTS

9.1 Inclusion Criteria

9.1.1 General inclusion criteria

1. Provision of written informed consent to participate in this investigational study.
2. Histological or cytological confirmation of Stage IIIb or Stage IV (unresectable) NSCLC.
3. ECOG performance status 0 or 1.
4. Age 18 years or older at the time of consent.
5. Female patients of childbearing potential must have a negative serum pregnancy test within 7 days prior to taking their first dose of BGB324. Male patients and female patients of reproductive potential must agree to practice highly effective methods of contraception (such as hormonal implants, combined oral contraceptives, injectable contraceptives, intrauterine device with hormone spirals, total sexual abstinence, vasectomy) throughout the study and for ≥3 months after the last dose of BGB324. Female patients are considered NOT of childbearing potential if they have a history of surgical sterility, including tubal ligation, or evidence of post-menopausal status defined as any of the following:
 - Natural menopause with last menses >1 year ago.
 - Radiation induced oophorectomy with last menses >1 year ago.
 - Chemotherapy induced menopause with last menses >1 year ago.

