- c. Triplicate 12-lead ECG, at least 5 minutes apart, after resting for \geq 10 minutes in supine position during screening and during each visit (pre-dose). Patients who re-start BGB324 following interruption for QTc prolongation should also have ECGs performed according to this schedule.
- d. For women of child-bearing potential to be repeated every 3 months, or if possibility of pregnancy is identified. A serum test must be performed at screening and the EOS visits; interim tests may be performed on urine samples.
- e. Unless conducted as part of the screening procedures within 3 days prior to Day 1.
- f. Clinical chemistry laboratory parameters: potassium, calcium, uric acid, electrolytes, blood urea nitrogen, total protein, total bilirubin, alanine aminotransferase, aspartate aminotransferase, creatinine, creatine phosphokinase, alkaline phosphatase, albumin, phosphorus, glucose, magnesium (plus amylase and lipase during screening ONLY).
- g. Hematology laboratory parameters: full blood count including differential white cell count, hemoglobin, hematocrit and platelets.
- h. Coagulation parameters: prothrombin time and/or international normalized ratio, activated partial thromboplastin time.
- i. Dipstick measurement of blood, nitrite, glucose, ketones, leukocytes, protein and pH. (Microscopic analysis is not required unless clinically indicated).
- j. Blood sampling for the determination of BGB324 / erlotinib in plasma will be collected in accordance with Table 6.
- k. In consenting patients (Arms A, B and C), tissue specimens may be collected for analysis of pharmacodynamics endpoints of Axl inhibition. The baseline tissue specimen should be collected after enrollment within 28 days before the first dose of BGB324. The on-study tissue collection may be performed any time after 14 days of continuous exposure to BGB324 in Cycle 1 or in Cycle 2. The EOS tissue collection should be made at the time of disease progression and prior to the end-of-study visit (derived from the lesion exhibiting disease progression). Detailed procedures for the collection, processing, storage and shipment of the samples will be provided in the laboratory manual.

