10.1 Procedures at each Visit

10.1.1 Screening and enrollment

Patients must provide written informed consent before any screening procedures are performed. The screening period covers up to 28* days prior to the first dose of BGB324.

During screening, the following procedures will be performed:

- Demographics.
- Medical history.
- Cancer history and treatments (medications and surgeries).
- EGFR mutation recorded
- T790M status confirmed in the screening period (Arm B)⁴
- Performance status assessment (ECOG).
- Physical examination.
- Vital signs (including height and weight)
- Serial 12-lead ECGs, in triplicate.
- Serum pregnancy test, if applicable.
- Clinical chemistry, (including amylase and lipase), hematology, urinalysis, coagulation
- Echocardiogram or MUGA scan.
- Disease assessment.
- Review of inclusion/exclusion criteria.

Male patients and female patients of reproductive potential must agree to practice highly effective methods of contraception throughout the study and for ≥3 months after the last dose of BGB324. Highly effective methods of contraception are defined as:

- Hormonal implants, combined oral contraceptives, injectable contraceptives.
- An intrauterine device with hormone spirals.
- Tubal ligation.
- True total sexual abstinence.
- Vasectomy.

If it is not possible to use one of these highly effective methods of contraception, 2 barrier methods used simultaneously are acceptable.

The following baseline samples should be taken in the 28 days before the first dose of BGB324 after the patient has been confirmed as otherwise eligible:

- Blood collection for PD (Arms A, B, and C only).
- Tissue collection for PD (consenting patients only) (Arms A, B, and C).

Patients who meet all inclusion/exclusion criteria will be allocated a study-specific patient number.

10.1.2 Cycle 1

All AEs and concomitant medication use will be recorded throughout the cycle.

⁴ The screening period for Arm B may be extended to allow for confirmation of T790M status all other assessments are to be conducted in the 28-day screening period. Patients who have previously been treated with a T790M inhibitor (i.e., osimertinib) and who subsequently progressed will not require T790M testing.

In addition, tissue (in consenting patients) and blood will be collected for pharmacodynamic assessment at one on-study time point after 14 consecutive days of BGB324 administration either in Cycle 1 or Cycle 2 (Arms A, B, and C).

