13.1.2 Serious adverse event

An SAE is any AE that meets any of the following criteria:

- Is fatal (i.e., the AE actually causes or leads to death).
- Is life-threatening (i.e., the AE, in the view of the Investigator, places the patient at immediate risk of death). This does not include any AE that had it occurred in a more severe form or was allowed to continue might have caused death.
- Requires or prolongs inpatient hospitalization, with exception of those events described in Section 13.4.7.
- Results in persistent or significant disability/incapacity (i.e., the AE results in substantial disruption of the patient's ability to conduct normal life functions).
- Congenital anomaly/birth defect in a neonate/infant born to a mother exposed to study drug.
- Is a significant medical event in the Investigator's judgment (e.g., may jeopardize the patient or may require medical/surgical intervention to prevent one of the outcomes listed above).

The terms *severe* and *serious* are not synonymous. Severity refers to the intensity of an AE (rated as mild, moderate, severe or life threatening or according to NCI CTCAE criteria Version 4.03 [Appendix 4]; see Section 13.3.1). The event itself may be of relatively minor medical significance (such as severe headache without any further findings). Severity and seriousness need to be independently assessed for each AE recorded on the eCRF.

SAEs must be reported by the Investigator to the Sponsor immediately (i.e., no more than 24 hours after learning of the event; see Section 13.5 for reporting guidelines).

The Investigator is responsible for ensuring that all AEs are recorded on the AE eCRF pages and appropriately reported to the Sponsor in accordance with instructions provided.

For each AE recorded on the AE eCRF, the Investigator will make an assessment of seriousness, severity (see Section 13.3.1), and causality.

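### The duty to report pregnancies ends 28 days after the last BGB324 dose, although the protocol requires contraception for at least 3 months, and neither document explains the difference

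*Protocol*

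**What the plan says.** Section 13.7.1 sets out who is covered: "In the event of a pregnancy occurring in female patients, or in the partners of male patients during the study, the pregnancy must be reported". It then fixes the period: "The reporting period for pregnancies will start with the first administration of BGB324 and end 28 days after the final administration of BGB324". Its closing sentence asks for consent to follow up a pregnancy when the patient leaves before term. That concerns a pregnancy already known and does not lengthen the period for new ones.

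Inclusion criterion 5 (Section 9.1.1, repeated in the synopsis) requires highly effective contraception from male patients and from female patients of reproductive potential, "throughout the study and for ≥3 months after the last dose of BGB324". Section 10.1.1 repeats the rule.

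Sections 8.6 and 8.9 place the EOS visit 28 days after the last dose, and Section 10.1.5 includes a serum pregnancy test at that visit. Table 5, footnote d, says: "A serum test must be performed at screening and the EOS visits; interim tests may be performed on urine samples". The visit-window row of Table 5 allows 7 days around the EOS visit. No pregnancy test is scheduled later.

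The SAP adds no rule on pregnancy reporting. It lists pregnancy test results, and its adverse event period also ends 28 days after the last dose (SAP 5.8.1).

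**The concern.** The contraception rule asks both sexes to avoid conception for at least 3 months after treatment. The reporting rule covers the same two groups, female patients and partners of male patients, but stops at 28 days. Neither document gives the basis for either period.

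A site following Section 13.7.1 as written therefore has no duty to notify the sponsor of a pregnancy that arises after day 28, even though the patient is still under the contraception requirement. At stake is complete safety information on pregnancies after exposure to an investigational drug. No endpoint, analysis population or decision rule is involved.

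**Working it through.** The plan states no figure that could be reproduced here, so the check compares the stated periods and then looks for other provisions that might close the gap.

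**Inputs**
- Reporting period after the last dose: 28 days (13.7.1).
- Contraception after the last dose: at least 3 months (9.1.1 criterion 5; 10.1.1).
- EOS visit and serum test: nominally day 28, with a 7-day window (8.9; 10.1.5; Table 5).
- Assumption: three calendar months are 89 to 92 days, depending on the start date.

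**Gap between the two periods** = contraception days − 28; share = gap ÷ contraception days.

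| 3 months taken as | Gap (days) | Share of calendar time |
|---|---|---|
| 89 days | 89 − 28 = 61 | 61/89 = 68.5% |
| 90 days | 90 − 28 = 62 | 62/90 = 68.9% |
| 92 days | 92 − 28 = 64 | 64/92 = 69.6% |

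The contraception rule is a minimum, so these are gaps against the shortest period it allows. Pregnancies on treatment are covered and do not enter the calculation.

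**EOS test.** The latest permitted EOS visit is 28 + 7 = day 35. A positive serum test on days 29 to 35 comes from a test the protocol requires, yet its date lies after the reporting period has closed. Section 13.7.1 does not say whether the 28 days refer to conception, detection or the site's awareness. A pregnancy conceived before day 28 and recognised later is therefore ambiguous too.

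**Other provisions that might close the gap**
- Section 13.1.2 counts this as a serious adverse event (SAE): "Congenital anomaly/birth defect in a neonate/infant born to a mother exposed to study drug". It needs an adverse birth outcome, and as worded it does not clearly reach the pregnancy of a male patient's partner.
- Section 13.5 says: "Study drug-related SAEs should continue to be reported indefinitely"; Section 13.2 agrees. This applies only to SAEs judged drug-related.
- Section 13.6 provides for expedited reporting of suspected unexpected serious adverse reactions after the study, and for prompt communication of other safety information that could change the risk-benefit evaluation.

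Together these could bring in a harmful outcome thought to be related to the drug. None captures the pregnancy itself or a normal outcome.

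**The case against.** The strongest reply is that a contraception precaution and a reporting duty are separate rules, and a site can obey both in full. The 28-day limit also matches the adverse event period, the routine SAE period and the EOS visit. This stands: the protocol does not contradict itself in the sense of asking for two incompatible things. What remains is an unexplained mismatch.

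Three stronger readings are tempting, and the documents do not support them.

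- A reader might infer that most of the reproductive risk is left uncovered. The protocol never says that months 2 and 3 carry risk; that is an inference from the contraception rule. The only exposure data point to little remaining drug. Section 6.2.2 gives a mean terminal half-life of 45.6 to 88.7 hours, so 28 days (672 hours) is 672/88.7 = 7.6 to 672/45.6 = 14.7 half-lives, and at 7.6 about 0.5% of the drug remains. These are single-dose data in healthy men. They say nothing about effects that outlast exposure, and the protocol does not use them to justify the shorter period.
- A reader might infer that such pregnancies will go unreported. The text shows only that 13.7.1 does not require the report. A site may still report voluntarily.
- A reader might infer that a harmed infant would be missed. The SAE rules could bring in an anomaly directly, within the limits set out above.

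It is also fair to say that numbers would be small. The study plans about 60 patients with Stage IIIb or IV disease, with contraception as an entry condition. The documents give no basis for an expected count.

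**Conclusion.** The point holds as a minor gap in safety reporting. Under 13.7.1 a pregnancy in about the last 61 to 64 days of the minimum contraception period need not be reported. This rests on reading 3 months as 89 to 92 days and on the current text of both documents, in which no other rule extends pregnancy reporting. The share of about 69% describes calendar time only; it should not be read as a share of risk, exposure or expected pregnancies. The difficulty with an EOS test on days 29 to 35 stands even if 28 days is long enough pharmacologically, because it comes from the protocol's own visit window. The other safety rules reduce the consequence without removing the gap.

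**What to change.** Reconcile Section 13.7.1 with inclusion criterion 5 (synopsis and 9.1.1) and Section 10.1.1. Either extend the duty to report pregnancies the site learns of, so that it covers the contraception period the protocol itself sets and any positive EOS test, or state why the shorter period is enough. In either case, say whether the period refers to conception or to detection. No view is taken here on how long contraception should last.

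Matching the periods would move the end of reporting from day 28 to at least day 89 to 92. The change takes a sentence or two and brings occasional reports after the EOS visit. It needs no new visits or tests, and so it remains a passive duty: with no scheduled contact after EOS, it would catch only what patients or partners tell the site. Active follow-up would cost more and is not proposed. The SAP analyses need no change.
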